3. Record the adverse effects of the different pharmacological therapies reported in the different groups throughout their follow-up.
4. Evaluate the lung function of the different groups at 3 months after discharge, 6 months and 12 months after discharge.

METHODS

a) Location of the study.

National Institute of Respiratory Diseases, Ismael Cosío Villegas México.

Smoking and COPD Research Department.

b) Description of the population:

Inclusion criteria:

1. Over 18 years of age.
2. Active smokers (smoking more than 100 cigarettes in their entire life and having consumed cigarettes in the last 30 days)
3. Hospitalized subjects with acute or chronic lung disease.
4. Signing of informed consent.

Exclusion criteria:

1. Subjects with pharmacological treatment to stop smoking during recruitment or in the last month.
2. Contraindications to the use of pharmacological therapy. (Annex is attached the contraindications for the use of medications)
3. Subjects who cannot maintain follow-up.

Elimination criteria:

1. In an analysis by intention to treat, there will be no elimination of subjects after randomization.

Sample size:

The sample size calculation is carried out by difference between proportions, with a confidence level of 95%, power of 80%, unilateral, with an observed proportion of 65% and an expected proportion of 80% for the combination of pharmacological therapy; 50 subjects are required for each group; If a loss of participants is estimated at 25%, 67 subjects are required for each group. The sample size was carried out in the WinEpi 2006 program.

c) Outcome variables and description of other study variables.

Outcome variable:

-Abstinence: abstinence from tobacco is defined as its suspension 12 months after hospital discharge, corroborated by detection of exhaled carbon monoxide less than 7 ppb and/or detection of cotinine in urine (positive).

-Active smoker: defined as an active smoker who has consumed more than 100 cigarettes in his or her entire life and who has consumed cigarettes in the last 30 days.

-CBT (cognitive behavioral therapy) is a model for treating problematic behaviors that focuses primarily on identifying and changing maladaptive patterns of behavior and thoughts, including problem-solving and coping skills rooted in relapse prevention theory, along with the cognitive restoration of maladaptive thoughts to regulate emotions and is combined with the recommendations of the Clinical Practice Guideline (CPG) for tobacco.

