(14)

-Acute or chronic lung disease: Acute or chronic lung disease will be considered by medical diagnosis.

-Exhaled carbon monoxide: a value greater than or equal to 7 ppb is defined as positive (subject with active smoking).

-Cotinine in urine: defined as positive (subject with active smoking) positive test (qualitative test)

-Nicotine dependence (Fagerström Questionnaire): mild, moderate and severe.

-Withdrawal symptoms questionnaire.

-Nicotine Craving Questionnaire (Urge to smoke, understood as a physiological and motivational state that drives the desire to smoke tobacco).

-Adverse reactions questionnaire.

-Respiratory symptoms questionnaires (PLATINO).

-Pulmonary function tests (pre- and post-bronchodilator spirometry, carbon monoxide diffusion, and 6-minute walk)

-Beck Anxiety and Depression Questionnaires.

Procedures for collecting information using instruments and data quality control methods.

Data Capture.

a)

b) 1-Subject identification (inclusion/exclusion criteria)

c) 2-Signature of informed consent

d) 3-Randomization of the drug (2 groups: a-nicotine patches, b-combination: nicotine patches + bupropion)

e) 4-Start hospitalization treatment

f) - Processes: Medications are given in a personalized way during hospitalization; brief advice is given, and questionnaires and measurements of exhaled CO and cotinine in urine are performed (treatment start day is day 0). The pharmacological treatment given to the subject will be for at least 12 weeks.

g) 5-Monitoring during hospitalization to provide medications

- h) 6-Upon discharge, an appointment is made at the Smoking Clinic within the first 14 days of discharge, and anti-smoking treatment for home use and brief advice will be provided.
- i) 7-First appointment at the Smoking Clinic
- j) - Processes: brief advice; intake of exhaled CO and cotinine in urine). It is scheduled to begin cognitive behavioral therapy (CBT) in a group, which lasts ten sessions, two times a week, with mixed modality (online or in-person).
- k) 8-Start CBT in the next two weeks after discharge.
- l) 9- Second appointment at the Smoking Clinic at the end of therapy (3 months after discharge)
- m) - Processes: brief advice; questionnaires and measurement of exhaled CO and cotinine in urine are performed; pre- and post-bronchodilator spirometry, carbon monoxide diffusion, 6-minute walk.
- n) 10-Third appointment at the Smoking Clinic 6 months after discharge:

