- o) - Processes: brief advice; questionnaires and measurement of exhaled CO and cotinine in urine are performed; pre- and post-bronchodilator spirometry, carbon monoxide diffusion, 6-minute walk)
- p) 11-Fourth appointment at the Smoking Clinic 12 months after discharge
- q) - Processes: brief advice; questionnaires and measurement of exhaled CO and cotinine in urine are performed; pre- and post-bronchodilator spirometry, carbon monoxide diffusion, 6-minute walk)
- r) The information collection will be carried out through the INER RedCAP platform, which has security mechanisms for the data obtained and methods for adequate control. The protocol researchers will carry out data capture.

Results analysis plan.

1- A retrospective analysis was carried out on hospitalized patients with a history of active smoking, with the following characteristics: 40% of the patients evaluated had low dependence on nicotine, and 60% had moderate and severe dependence. Of the patients evaluated, 72% were male, and 28% were female. Proportional allocation is carried out for stratified sampling, Stratified randomization for sex (man and woman), and for low and moderate/severe dependence

2- Statistical analysis methods according to the type of variables: the variables will be analyzed according to their type of distribution and whether they are quantitative or qualitative, by student's t or chi2 as appropriate. A descriptive analysis will be carried out on each of the variables. Subsequently, a comparative analysis will be carried out between the 2 groups included, using ANOVA or Kruskal Wallis, depending on their distribution. The analysis of the main objective will be carried out by intention to treat according to the treatment granted and randomization. Randomization was stratified by level of nicotine dependence and sex. There will be no blinding. The primary outcome will be abstinence at 12 months, and its association with the randomized treatment group will be seen. As a complementary analysis, a per-protocol analysis will be performed according to the treatment received. Finally, through multivariate analysis by logistic regression, abstinence or non-abstinence at one year was analyzed depending on the treatment received, adjusted for the different covariates such as sex, age, smoking rate, and level of dependence.

3-The statistical analysis will be carried out using the STATA V13 statistical package.

ETHICAL CONSIDERATIONS

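### The planned 50 per group (67 after losses) does not give 80% power for 65% versus 80%, even with the one-sided 5% test assumed; the analysis plan states neither the alpha nor the side of the primary test

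*Combined protocol and SAP*

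**What the plan says.** Under METHODS, b), Sample size, the method is given: "The sample size calculation is carried out by difference between proportions". The settings are "with a confidence level of 95%, power of 80%, unilateral", and the rates are "with an observed proportion of 65% and an expected proportion of 80% for the combination of pharmacological therapy". The result is that "50 subjects are required for each group", and then: "If a loss of participants is estimated at 25%, 67 subjects are required for each group". The data-capture steps confirm two randomised arms: "Randomization of the drug (2 groups: a-nicotine patches, b-combination: nicotine patches + bupropion".

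Results analysis plan, item 2, makes 12-month abstinence the primary outcome, analysed by intention to treat without blinding. Variables are to be compared "by student's t or chi2 as appropriate". There is also an adjusted model: "through multivariate analysis by logistic regression, abstinence or non-abstinence at one year was analyzed". No alpha or side is stated for any of these tests. The one-sided choice appears only in the sample-size paragraph.

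**The concern.** Fifty per group is small for a 15-point difference between two randomised groups at these rates. In addition, the one-sided choice made for planning is not carried into the analysis plan, where the named methods are ordinarily reported two-sided.

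At stake is how the result will be read. If the trial finds no significant difference, readers will weigh that against a stated 80% chance of detecting the planned effect. If the real chance is between about two in five and three in five, a null result says much less about whether adding bupropion helps. Because the trial is open-label, the side of the primary test should also be fixed in writing before the data are analysed.

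**Working it through.** **Inputs, all from the sample-size paragraph:** p1 = 0.65, p2 = 0.80, difference d = 0.15, alpha = 0.05 one-sided, power 0.80, two equal groups, 25% loss. Normal quantiles: 1.6449 (one-sided 5%), 1.9600 (two-sided 5%), 0.8416 (80% power).

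**1. Reproducing the plan's figures.** The loss step is right: 50 / (1 − 0.25) = 66.7, rounded up to 67. The base figure is not reproduced. The two-group formula is

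n = [z_a·√(2·p̄·(1 − p̄)) + z_b·√(p1(1 − p1) + p2(1 − p2))]² / d²

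with p̄ = 0.725, so the two roots are √0.39875 = 0.6315 and √0.3875 = 0.6225.

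- One-sided: (1.6449 × 0.6315 + 0.8416 × 0.6225)² / 0.0225 = (1.0387 + 0.5239)² / 0.0225 = 108.5, so 109 per group.
- Two-sided: (1.2377 + 0.5239)² / 0.0225 = 137.9, so 138 per group.

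Other standard versions agree. One-sided they give 107 (unpooled variance), 108 (arcsine) and 122 (continuity-corrected). Two-sided they give 136, 137 and 151. After 25% loss, 109 becomes 146 and 138 becomes 184.

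**2. Where 50 may come from.** At the stated 5% and 80%, the only formula tried that returns 50 is the one-sample, one-sided one, which tests a single group against a fixed null of 80% with a true rate of 65%:

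(1.6449 × √0.16 + 0.8416 × √0.2275)² / 0.0225 = (0.6579 + 0.4014)² / 0.0225 = 49.9.

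With the null at 65% it gives 55.9. The two-group formula reaches 50 only if the inputs change: a one-sided alpha of 20% gives (0.5315 + 0.5239)² / 0.0225 = 49.5, which conflicts with the stated 95% confidence. The documents do not include the program output, so the source of the 50 remains an inference.

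**3. Power at the planned sizes.** Power = Φ{[d·√n − z_a × 0.6315] / 0.6225}. For n = 67, d·√n = 1.2278. For n = 50, it is 1.0607.

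| Analysed per group | One-sided 5% | Two-sided 5% |
|---|---|---|
| 67 | Φ(0.304) = 61.9% | Φ(−0.016) = 49.4% |
| 50 | Φ(0.035) = 51.4% | Φ(−0.284) = 38.8% |

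Exact binomial enumeration of the uncorrected chi-square gives 62.9% and 49.6% at 67, and 52.2% and 39.3% at 50.

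**4. Splitting the shortfall at 67 per group.** From 80% to 61.9% is 18.1 points, present under the plan's own one-sided test. From 61.9% to 49.4% is a further 12.5 points, due to two-sided testing. The total is 30.6 points. For comparison, a correctly sized one-sided trial of 109 per group would still have 70.1% power if tested two-sided.

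**5. Detectable rate against 65%, at 80% power.** With 67 per group: about 84% one-sided and 86% two-sided. With 50 per group: about 86% and 88.5%.

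**6. Sensitivity to missing outcomes (an assumption, because no rule is given).** If the 25% lost were counted as smokers, the rates become 0.75 × 65% = 48.75% and 0.75 × 80% = 60%. Power at 67 per group is then about 37% one-sided or 26% two-sided.

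**The case against.** A reader might infer that the plan contradicts itself on sidedness, and that this mismatch is what takes 80% power down to 49%. The documents support neither step.

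First, the analysis plan never says two-sided. For a single two-group comparison, a directional 5% test can be taken from the signed version of the same statistic, so the sample-size paragraph and the analysis plan can be reconciled. Two-sided testing is inferred from how chi-square and logistic regression are usually reported. What is documented is silence on alpha and side.

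Second, sidedness is the smaller cause, as the 70.1% at 109 per group shows. Declaring a one-sided test would therefore not restore 80%: power would still be 62% with 67 analysed or 51% with 50.

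It is also fair to say that the plan chose a one-sided test openly, and nothing in the documents rules that out. It should not be treated as a fallback to a two-sided default.

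One part of the concern survives all of this: on the plan's own rates, alpha and one-sided test, 67 per group does not deliver 80%.

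**Conclusion.** The stated power is wrong for the primary comparison under every reading of the side of the test. On the plan's own one-sided 5% terms, it is about 62% if all 67 per group are analysed and 51% if the planned losses leave 50. Two-sided, it is about 49% and 39%. The sample size for 80% would be about 109 or 138 analysed per group, roughly two to three times the stated 50. The main fault is the base figure; the unstated side of the test is a second and smaller one.

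The power figures assume abstinence of 65% and 80% among those analysed, equal groups and an unadjusted comparison. They would be lower still if losses were counted as smokers. That the 50 came from a one-sample calculation is a plausible reading of the arithmetic and not something the documents state.

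**What to change.** Two changes of wording, both before analysis:

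- **Results analysis plan, item 2:** state the alpha and side of the primary test of 12-month abstinence, consistent with the sample-size paragraph. If the one-sided 5% test is kept, say so here. If a two-sided test is preferred, change both places.
- **Sample size:** replace the 80% with the power for that choice. One-sided, this is about 62% with 67 analysed per group and 51% with 50; two-sided, about 49% and 39%. Alternatively, state the detectable difference, for example about 86% versus 65% with 67 per group, two-sided. Correct or explain the 50, and say whether the 67 or the 50 is the number expected in the primary analysis.

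If a rule for missing outcomes is added, the power should be restated under that rule.

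No extra enrolment and no change to trial conduct is needed. The cost is a less favourable stated power and more cautious reading of a null result.

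### The stated inputs require at least 107 evaluable patients per group, not 50; one-sided power is about 52% at 50 and at most about 63% at 67, against the stated 80%

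*Combined protocol and SAP*

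**What the plan says.** The Sample size paragraph (METHODS, b) Description of the population) describes a calculation for a difference between proportions at 95% confidence, with "power of 80%, unilateral, with an observed proportion of 65% and an expected proportion of 80% for the combination of pharmacological therapy". Its result is that "50 subjects are required for each group; If a loss of participants is estimated at 25%, 67 subjects are required for each group". It names the program used but shows no formula.

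The design is a concurrent two-arm comparison. Step 3 of the Data Capture list randomises to "2 groups: a-nicotine patches, b-combination: nicotine patches + bupropion". Item 2 of the Results analysis plan makes 12-month abstinence the primary outcome and says: "The analysis of the main objective will be carried out by intention to treat". The Elimination criteria add that "there will be no elimination of subjects after randomization".

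The test for the primary comparison is described only in general terms: item 2 assigns Student's t "or chi2 as appropriate" by type of variable and does not say whether the test is one- or two-sided.

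**The concern.** All the inputs for a two-proportion sample size are given, so the result can be checked without any outside figure. A 15-point difference between 65% and 80% normally needs about 100 or more patients per group, even with a one-sided test. A result of 50 is less than half of that, which is too large a gap to come from rounding or from the choice among standard formulas.

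This paragraph is the only numerical justification for the size of the trial, and it concerns the primary outcome. If the number is wrong, the trial has a much higher chance of missing the benefit it was designed to find, and a non-significant result would be read as coming from a trial with 80% power.

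**Working it through.** **Inputs.** From the Sample size paragraph: p1 = 0.65 (observed), p2 = 0.80 (combination), one-sided α = 0.05, power 80%, loss 25%. Equal allocation is implied by the equal group sizes. The text does not say which group the 65% describes; it is taken here as the nicotine-only group. Then d = 0.15, d² = 0.0225, z(0.95) = 1.645 and z(0.80) = 0.842.

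**The plan's own figures.** The loss step reproduces: 50/0.75 = 66.7, rounded up to 67. The 50 does not.

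**Two-group formulas, one-sided 5%, per group:**

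- Unpooled: (1.645 + 0.842)² × (0.65×0.35 + 0.80×0.20)/0.0225 = 6.183 × 0.3875/0.0225 = 106.5, so 107.
- Arcsine: h = 2·asin√0.80 − 2·asin√0.65 = 0.339; 2 × 6.183/h² = 107.7, so 108.
- Pooled: mean rate 0.725; [1.645·√(2×0.725×0.275) + 0.842·√0.3875]²/0.0225 = 108.5, so 109.
- Pooled with continuity correction: 121.5, so 122.
- Pooled variance in both terms gives 110, and the log odds ratio formula gives 112.

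**Enrolment with 25% loss:** 107/0.75 = 142.7, so 143; 109/0.75 = 145.3, so 146; 122/0.75 = 162.7, so 163.

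**Power at the planned sizes.** The normal approximation is Φ{[d√n − 1.645·√0.39875]/√0.3875}. The exact column sums the binomial probabilities over the rejection region of the one-sided pooled z test.

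| Analysed per group | Normal approximation | Exact |
|---|---|---|
| 50 | 51.4% | 52.2% |
| 67 | 61.9% | 62.9% |
| 109 | 80.2% | 80.4% |

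The last row confirms that the formulas reach the intended 80%.

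**Difference detectable with 80% power from 65%, one-sided.** At 50 per group the combination rate must be 85.9% to 86.1%, about 21 points. At 67 it must be 83.5% to 83.6%, about 18.5 points. The plan assumes 15.

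**Where 50 might come from.** A one-sample formula with 80% as a fixed reference and 65% as the alternative gives (1.645·√0.16 + 0.842·√0.2275)²/0.0225 = 49.9. With 65% as the fixed reference it gives 55.9. The two-group pooled formula gives 49.5 at a one-sided α of 0.20, which contradicts the stated 95% confidence. The documents do not show which route was used, if any of these.

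**Losses counted as smokers (an assumption; the documents give no rule for missing outcomes).** If 65% and 80% apply to patients who are followed up, the intention-to-treat rates become 0.75 × 0.65 = 48.75% and 0.75 × 0.80 = 60%. One-sided power at 67 per group is then about 37%.

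**If the primary test is two-sided.** The need is 135.2 (136, unpooled) to 137.9 (138, pooled) evaluable, or 182 to 184 enrolled per group. Power is about 39% at 50 and about 50% at 67.

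**The case against.** The program may have used a method that the plan does not describe, and the one-sample match at 49.9 suggests a consistent calculation and not a typing error. This does not rescue the figure. A one-sample formula treats one rate as known without error, whereas both rates here are estimated from randomised patients. The match may also be coincidence, and the finding does not depend on it.

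A second argument is that intention to treat keeps all 67, so power at 50 is irrelevant. That is fair as far as it goes, but even complete outcomes on all 67 at unchanged rates give only about 63%. If the planned 25% are lost and only completers are analysed, the number falls back to 50 and power to about 52%.

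Some points on the other side do stand:

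- The range 107 to 109 is a minimum. A continuity-corrected calculation needs 122, and a one-sided Fisher exact test would have only about 42% power at 50 and 55% at 67.
- The 37% figure counts losses twice if the 65% and 80% already treat lost patients as smokers. The plan does not say, so that figure illustrates the risk and carries no weight in the conclusion.
- The sample size is explicitly one-sided, and the general mention of chi-square does not commit the primary test to two sides. The missing sidedness is a smaller, separate gap.

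**Conclusion.** The concern holds with high confidence. From the plan's own inputs, 50 evaluable per group is less than half the smallest standard two-group result of 107. The stated 80% power is not delivered at 50 or at 67 per group. If the assumed effect is real, the one-sided chance of missing it is about 48% with 50 evaluable and about 37% with all 67 analysed, against the stated 20%.

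This rests on equal allocation, on 65% being the nicotine-only rate, and on a one-sided 5% test, which is the reading most favourable to the plan. The figure at 67 also assumes complete outcomes at unchanged rates. The rates themselves are not disputed; the error lies between the stated inputs and the stated result. How the 50 arose remains an inference.

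**What to change.** Correct the Sample size paragraph in one of two ways.

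1. **Keep 67 per group and restate the power.** Replace the 80% claim with about 52% one-sided power at 50 evaluable, and about 63% if all 67 have outcomes at the assumed rates. Give the differences detectable with 80% power: about 21 points and about 18.5 points. The cost is a rewritten paragraph and a less favourable stated power, with no extra patients.
2. **Keep 80% power and restate the size.** Plan 107 to 109 evaluable per group, or 143 to 146 enrolled with 25% loss. Total enrolment rises from 134 to 286–292, which is 152 to 158 more patients. If the continuity-corrected formula is chosen, the figures are 122 evaluable and 163 enrolled per group.

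In either case, show the formula, name the group to which the 65% belongs, and say whether the power refers to the 50 evaluable or to all 67 randomised. For the latter, also say how missing 12-month outcomes are counted and whether the assumed rates already reflect that rule.

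As a secondary point, state one sidedness for both the sample size and the primary test. If that is two-sided, the need becomes 136 to 138 evaluable, or 182 to 184 enrolled, per group.

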Nicotine Replacement Therapy (NRT) helps combat nicotine withdrawal symptoms by providing users with nicotine in long-acting (patch) or short-acting (mask gum, lozenges, inhaler, nasal spray) form. Use of NRT in any form increases smoking abstinence by 60% compared to placebo (RR 1.60, 95% CI 1.53–1.68). To increase effectiveness, the nicotine patch can be combined with short-acting NRT, which is more effective than using a form of NRT (RR 1.34, 95% CI 1.18–1.51) (10). Bupropion increases norepinephrine and dopamine levels and is approved as an antidepressant for smoking cessation. Increases smoking cessation rates compared to placebo (OR 1.75, 95% CI 1.52 to 2.01) (8.9). Varenicline is a partial nicotinic receptor agonist that doubles smoking abstinence rates compared to placebo (RR 2.24, 95% CI 2.06–2.43). (10) These results have been obtained in smokers treated on an outpatient basis. The study of the effectiveness of these different treatments in hospitalized subjects has been little and marginally analyzed.(6) Among the studies carried out, it shows that hospitalized subjects who received treatment for smoking cessation and support had abstinence rates greater than 6 months. The analysis carried out in this study does not differentiate by type of pharmacological treatment. The predominant pharmacological treatment was NRT. (11) Smoking cessation in hospitalized patients has been associated with lower rates of postsurgical complications, better tissue healing and proliferation, and reversibility of the attenuation of inflammation mechanisms. (12,13)

Hospitalization is a vital scenario to address tobacco consumption for various reasons and benefits; among the most important are the prohibition of smoking on the hospital premises and the special availability for quitting that the smoker has during admission to a hospital admission promotes subsequent tobacco cessation because a severe illness, primarily if related to tobacco, can increase smokers' motivation to quit.

MAIN OBJECTIVE

Our objective will be to analyze the effectiveness of the combination of bupropion and nicotine versus nicotine replacement therapy to quit smoking in hospitalized subjects 12 months after discharge.

SPECIFIC OBJECTIVES

1. Analyze the effectiveness of the combination of pharmacological therapies to quit smoking in hospitalized subjects 3, 6 and 12 months after discharge.
2. Evaluate the symptoms and signs of withdrawal in the different groups throughout their follow-up.

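### The 12-month abstinence definition accepts a positive urine cotinine as corroboration, although the same section defines that result as active smoking, and the way the two tests combine is left open

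*Combined protocol and SAP*

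**What the plan says.** In METHODS, c) Outcome variables, the Abstinence entry requires that tobacco has been stopped at 12 months after discharge, "corroborated by detection of exhaled carbon monoxide less than 7 ppb and/or detection of cotinine in urine (positive".

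The same list then defines each test:

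- Exhaled CO: "a value greater than or equal to 7 ppb is defined as positive (subject with active smoking".
- Urine cotinine: "Cotinine in urine: defined as positive (subject with active smoking) positive test (qualitative test".

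The Results analysis plan, item 2, states "The primary outcome will be abstinence at 12 months" and "There will be no blinding". It gives no rule for combining the two tests or for resolving results that disagree. The data-capture steps schedule both tests at the 3-, 6- and 12-month visits.

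Two other passages bear on the point. Both arms receive nicotine patches, and "The pharmacological treatment given to the subject will be for at least 12 weeks" (Data Capture, step f). Specific objective 1 concerns the effectiveness of combined "pharmacological therapies to quit smoking in hospitalized subjects 3, 6 and 12 months after discharge", whereas the Abstinence entry names only month 12.

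**The concern.** The CO criterion agrees across the two places: below the cut-off supports abstinence, and at or above it means smoking. The cotinine criterion is reversed: one result supports abstinence in one entry and means active smoking in another. The word may be a drafting or translation slip, but no later passage corrects it.

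The connector is a second, separate gap. Both tests are done at the 12-month visit, so a participant can be clean on one and positive on the other, and the text does not say how to classify that person.

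This is the only place where the plan says how abstinence is to be established. If it is coded as written, the primary endpoint does not measure abstinence. If staff correct the sign informally, the connector is still open. In an unblinded trial whose own researchers capture the data, that choice could be made after results by arm are visible.

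**Working it through.** **Inputs.** Planned abstinence is 65% and 80%, from METHODS, b) Sample size: "with an observed proportion of 65% and an expected proportion of 80% for the combination of pharmacological therapy". That text does not tie the two rates to month 12; they are used here as true 12-month abstinence. Group size is 67, the plan's 50 allowing for 25% loss: 50 / (1 − 0.25) = 66.7, rounded up to 67. Whether 50 is itself right is a separate question and does not enter here. The plan gives no figure for test accuracy, false reporting or discordant results, so those below are assumptions.

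**Step 1. Classification of participants who report having stopped.** *Corrected* means that a negative cotinine corroborates.

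| Test results | Literal *and* | Literal *or* | Corrected *and* | Corrected *or* |
|---|---|---|---|---|
| CO < 7, cotinine negative | no | yes | yes | yes |
| CO < 7, cotinine positive | yes | yes | no | yes |
| CO ≥ 7, cotinine negative | no | no | no | yes |
| CO ≥ 7, cotinine positive | no | yes | no | no |

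No row is classified the same way under all four readings. Correcting the sign settles the first and last rows. The two discordant rows still depend on the connector.

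**Step 2. Literal readings, error-free tests, no nicotine medication at 12 months.** Let p be true abstinence and m the share of continuing smokers who say they have stopped, taken as equal in both arms.

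- Literal *and*: every true abstainer has a negative cotinine and every smoker has a high CO, so the rate is 0% in both arms. Abstainers rejected per 67: 67 × 0.65 = 43.6 and 67 × 0.80 = 53.6.
- Literal *or*: rate = p + m(1 − p), difference = 15(1 − m) points, and smokers accepted per 67 = 67(1 − p)m.

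| m (assumed) | Nicotine arm | Combination arm | Difference (points) | Smokers accepted per 67 |
|---|---|---|---|---|
| 0% | 65% | 80% | 15 | 0 and 0 |
| 20% | 72% | 84% | 12 | 4.7 and 2.7 |
| 50% | 82.5% | 90% | 7.5 | 11.7 and 6.7 |
| 100% | 100% | 100% | 0 | 23.5 and 13.4 |

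**Step 3. Corrected sign, connector still open.** With error-free tests, *and* and *or* both return 65% versus 80%. With imperfect tests they separate. Assume that abstainers have CO below 7 with probability 0.90 to 0.95 and a negative cotinine with probability 0.80 to 0.95, that the tests are independent, and that no smoker claims to have stopped.

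- *And*, low end: 0.90 × 0.80 = 0.72, giving 46.8% versus 57.6% (10.8 points). High end: 0.95 × 0.95 = 0.9025, giving 58.7% versus 72.2% (13.5 points).
- *Or*, low end: 1 − 0.10 × 0.20 = 0.98, giving 63.7% versus 78.4% (14.7 points). High end: 1 − 0.05 × 0.05 = 0.9975, giving 64.8% versus 79.8% (15.0 points).

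**Step 4. Imperfect tests when every smoker claims to have stopped (m = 100%).** Rate = p × P(accepted given abstinent) + (1 − p) × P(accepted given smoking). Three assumed accuracy sets were run, with smokers CO-positive 70–90% and cotinine-positive 95%, and abstainers CO-negative 90–95% and cotinine-negative 80–95%. Differences in points, combination minus nicotine alone:

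| Reading | Range of difference |
|---|---|
| Literal *and* | −3.6 to +1.3 |
| Literal *or* | −0.7 to −0.2 |
| Corrected *and* | +10.7 to +13.3 |
| Corrected *or* | +9.9 to +12.5 |

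The literal *or* row agrees with the zero difference in the last line of Step 2.

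**Step 5. Nicotine patches at 3 months (secondary).** Suppose the corrected *and* rule is also used at 3 months, patch nicotine turns the cotinine test positive, and a share q of abstainers in each arm is still on patches. Keeping 65% and 80% for illustration, the rate is p(1 − q): 48.75% versus 60% at q = 25% (11.25 points), and 32.5% versus 40% at q = 50% (7.5 points).

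**The case against.** The strongest reply is that nobody would apply the text literally. The variable list gives the direction of both tests, so staff would read the cotinine criterion as negative. The 0% result and the m series then describe a reading that is unlikely to be used, and under error-free tests the corrected rule returns the planned rates with either connector. This is fair as to the literal figures: they show that the written rule is unusable and do not forecast the result. It does not close the point, because correcting the sign leaves the connector open, and Step 3 shows that the connector alone can move the reported rates.

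Other objections affect the figures only:

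- The share m has no source in the documents and need not be equal between arms in an open-label trial. That stands; it is an assumption shown over its full range.
- Counts per 67 assume that everyone is assessed. With 50 per arm, the abstainers rejected under literal *and* would be 32.5 and 40, and the smokers accepted under literal *or* at m = 20% would be 3.5 and 2. The larger base fits the plan's rule that nobody is eliminated after randomization.
- Literal *or* does not remove all biochemical checking, since it still rejects CO ≥ 7 with a negative cotinine. Under error-free tests, however, it rejects no smoker who claims to have stopped.
- The patch issue is weaker. Treatment starts in hospital, so a 12-week course would normally end before a visit 3 months after discharge, and the primary endpoint is affected only if nicotine medication is still in use at month 12. The plan sets a minimum duration and no maximum, so the case can arise, but it is secondary.

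**Conclusion.** The concern holds. The primary-outcome definition contradicts the plan's own definition of a positive cotinine, and the combination rule is undetermined. Both findings come from the text alone and need no assumption. This must be fixed before outcome data are examined.

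The numerical size is conditional. Read literally, the endpoint either counts no error-free abstainer or shrinks the planned 15-point difference by the factor 1 − m. With the sign corrected, the connector choice moves measured abstinence by about 6 to 17 points in the nicotine arm (64.8 − 58.7 = 6.1; 63.7 − 46.8 = 16.9) under the assumed accuracies and truthful reporting. The documents do not give the frequency of discordant results, so the actual effect cannot be stated.

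**What to change.** In METHODS, c) Outcome variables, change the corroborating cotinine result to negative, so that it agrees with the cotinine entry in the same list, and replace the double connector with a single one. Possible wording:

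*Abstinence is reported suspension of tobacco 12 months after discharge, corroborated by exhaled CO below the cut-off and a negative urine cotinine. For a participant using nicotine medication at the visit, cotinine is not used and CO alone corroborates.*

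The choice of *and*, and of CO alone for nicotine users, is an example. What is needed is one explicit rule, dated before outcome data are examined. Add a sentence on classification when one of the two results is missing, and another saying whether the same definition applies at 3 and 6 months.

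The cost is a few sentences of protocol text. Both tests are already scheduled at the 3-, 6- and 12-month visits. The listed questionnaires do not name an item on current smoking status or on current nicotine-medication use; if they contain none, a short question on each is needed. The drawback of requiring both tests to be clean is that observed abstinence may be lower than with either test alone, so the rates assumed in the sample size should be checked against the rule chosen.
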